4.4. Secondary Endpoints Analysis

4.4.1. Key/Confirmatory Secondary Endpoint: Overall Survival

4.4.1.1. Definition of endpoint

Overall survival is defined as the time from randomization until death from any cause. If the participant is alive or lost to follow-up at the time of analysis, OS data will be censored on the last date the participant is known to be alive.

4.4.1.3. Sensitivity Analyses

One sensitivity analysis of OS is planned. Overall survival time for this analysis is defined as the time from the date of study enrollment to the date of death due to study disease. Survival time will be censored on the date the patient was last known to be alive for patients who have no reported event. For patients that have died due to reasons not related to the disease, survival time will be censored at the date of death.

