7.3. Lost to Follow-Up

A participant will be considered lost to follow-up if he/she repeatedly fails to return for scheduled visits and is unable to be contacted by the study site. Site personnel or designee are

expected to make diligent attempts to contact participants who fail to return for a scheduled visit or were unable to be followed.

Within legal and ethical boundaries, study site personnel or an independent third party will attempt to collect the survival status for all randomized participants who are lost to follow-up, including those who do not receive study treatment. Public sources may be searched for survival status information. The survival status will be documented, and the participant will not be considered lost to follow-up if survival status is determined.

Sponsor personnel will not be involved in any attempts to collect survival status information.

Discontinuation of specific sites or of the study as a whole are handled as part of Appendix 1.

8. Study Assessments and Procedures

Study procedures and their timing are summarized in the SoA.

Immediate safety concerns should be discussed with the Sponsor to determine if the participant should continue or discontinue study intervention.

Adherence to the study design requirements, including those specified in the SoA, is essential and required.

All screening evaluations must be completed and reviewed to confirm that participants meet eligibility criteria. The investigator will maintain a screening log to record details and to confirm eligibility or reasons for screening failure, as applicable.

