1.2. Study Design

postMONARCH is a Phase 3, global, multicenter, randomized, double-blind, placebo-controlled study in participants with HR+, HER2- advanced or metastatic breast cancer. This study will enroll adults who experienced relapse or disease progression on/after a CDK4 & 6 inhibitor and an aromatase inhibitor in the first-line setting or on/after CDK4 & 6 inhibitor with endocrine therapy in the adjuvant setting.

Approximately 350 participants will be equally randomized between 2 treatment arms and will be treated until disease progression or other discontinuation criteria are met.

- Arm A: abemaciclib plus fulvestrant
 - o abemaciclib 150 mg orally BID on Days 1 through 28 of each cycle
 - fulvestrant 500 mg IM on Cycle 1 Day 1 and Cycle 1 Day 15, then on Day 1 of Cycle 2 and beyond
- Arm B: placebo plus fulvestrant
 - o placebo BID on Days 1 through 28 of each cycle
 - fulvestrant 500 mg IM on Cycle 1 Day 1 and Cycle 1 Day 15, then on Day 1 of Cycle 2 and beyond
- Participants will be randomized using the following stratification factors:
 - geography CCI

- presence of visceral metastases (Yes versus No)
- duration on prior adjuvant/metastatic CDK4 & 6 inhibitor-based regimen

2. Statistical Hypotheses

Primary Hypothesis (Arm A versus Arm B): Multiplicity Adjustment

A gated hypothesis testing procedure will be used to ensure control of the familywise error rate at 0.025 (one-sided) across the 2 endpoints (PFS and OS). The primary endpoint of PFS will first be tested; the secondary OS will be tested only if statistical significance is achieved for PFS. Other endpoints will not be error controlled.

3. Analysis Sets

The populations for analysis are defined as follows.

| Population | Description |
|------------|--|
| Entered | All participants who sign the ICF |
| ITT | All participants randomly assigned to study treatment, regardless of whether they take any doses of study treatment, or if they take the correct treatment. Participants will be analyzed according to the treatment group to which they were assigned |
| Safety | All participants randomly assigned to study treatment and who take at least 1 dose of study treatment. Participants will be analyzed according to the study treatment they actually received |
| РК | All participants who have received at least 1 dose of abemaciclib, have at least 1 evaluable PK sample, and have sufficient dosing information |

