4.1.2. Handling of Dropouts or Missing Data

With the exception of dates, missing data will not be imputed. The method of imputation for any dates that are imputed is described in the relevant section.

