4.3.3. Sensitivity Analyses

Sensitivity analyses will be undertaken for calculation of the primary endpoint in order to evaluate the robustness of the analysis. The following sensitivity analyses will be performed for PFS:

- Using different rules for censoring (details provided in Table 3 below)
- Using an unstratified log-rank test and unstratified Cox model
- Using stratification factors based on the eCRF data if available
- Using a multivariate Cox regression model constructed by selecting variables among all the potential variables such as the variables used in the subgroup analyses, using stepwise selection method, with an entry p-value of 0.05 and an exit p-value of 0.1. The treatment factor will be kept out of the model throughout the covariate selection process and only added to the final model

CONFIDENTIAL

| Definition | Situation | Event/ Censor | Date of Event or Censor |
|---|--|------------------|---------------------------------|
| SA1: Ignoring absence of adequate postbaseline tumor assessment | No adequate postbaseline tumor assessment available and death reported after 2-scan intervals following randomization | Event | Death |
| SA2: Ignoring missing tumor assessments | PD or death documented after 2 or more missing scan intervals following last adequate tumor assessment or randomization (whichever is later) | Event | Earliest date of PD or death |
| SA3: Symptomatic progression as a PFS event | Symptomatic progression that is not radiologically confirmed per RECIST 1.1 criteria | Event | Date of symptomatic progression |

Table 3 PFS Censoring Scheme for Sensitivity Analyses

Abbreviations: PD = progressive disease; PFS = progression-free survival; RECIST 1.1 = Response Evaluation Criteria in Solid Tumors, version 1.1.; SA = sensitivity analysis.

Other sensitivity analyses for PFS may be conducted if deemed appropriate.

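### Does the single OS sensitivity analysis, which counts only deaths from the study disease, leave the overall survival result without a proper check?

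*SAP*

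**What the plan says.** SAP 4.4.1.1 defines the endpoint: "Overall survival is defined as the time from randomization until death from any cause". SAP Section 2 places OS behind PFS in a gated procedure: "the secondary OS will be tested only if statistical significance is achieved for PFS". No other endpoint is under error control.

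SAP 4.4.1.3 then states: "One sensitivity analysis of OS is planned". The clock starts at study enrollment, which Protocol Appendix 9 defines as assignment to treatment, so the origin is in effect randomization. Only deaths from the study disease are events. Patients with no reported event are censored when last known alive. For the remaining deaths the rule is: "For patients that have died due to reasons not related to the disease, survival time will be censored at the date of death".

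Two general provisions bear on cause of death. Protocol 7.3 covers participants lost to follow-up: "Public sources may be searched for survival status information". SAP 4.1.2 says: "With the exception of dates, missing data will not be imputed". Neither classifies a death whose cause is not known.

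For PFS, SAP 4.3.3 lists several checks, among them "Using an unstratified log-rank test and unstratified Cox model" and "Using stratification factors based on the eCRF data if available". SAP 4.4.1.2, where the main OS method would stand, and Table 4 are not in the public text. What they contain cannot be read, and it is not treated here as absent from the plan.

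**The concern.** A sensitivity analysis is usually expected to keep the question and vary an assumption behind the answer. The unstratified and eCRF-strata analyses of PFS do that. The OS analysis changes the event instead. It estimates the treatment effect on the hazard of dying from breast cancer, which is a different quantity from the effect on dying at all.

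Two things could be at stake. First, agreement between the two analyses might be presented as evidence that the OS result is robust, which it would not establish. The direction could also flatter the experimental arm: Protocol 8.2.6 records fatal ILD/pneumonitis with abemaciclib, and deaths judged to be due to toxicity are among those this analysis censors. Second, a death of unknown cause fits neither category in the text. It could be counted as an event, censored at the date of death, or censored when the patient was last known alive, and the choice could move the estimate.

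**Working it through.** The visible text gives no figure for OS deaths, the OS effect or cause-of-death shares, so there is no plan figure to reproduce. Every input below is an assumption used for scale, not a forecast.

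**1. How far can the two analyses differ?** Let p be the share of control-arm deaths not due to the disease, HRd the hazard ratio for disease deaths and HRo the hazard ratio for other deaths. With constant hazards,

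all-cause HR = (1 - p) × HRd + p × HRo.

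Take HRd = 0.85. Example: p = 0.10 and HRo = 2 give 0.90 × 0.85 + 0.10 × 2 = 0.765 + 0.200 = 0.965.

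| HRo | All-cause HR, p = 0.05 | All-cause HR, p = 0.10 | Disease-only HR |
|---|---|---|---|
| 0.5 | 0.833 | 0.815 | 0.85 |
| 0.85 | 0.850 | 0.850 | 0.85 |
| 1 | 0.858 | 0.865 | 0.85 |
| 2 | 0.908 | 0.965 | 0.85 |
| 3 | 0.958 | 1.065 | 0.85 |

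The disease-only analysis returns 0.85 throughout, as a cause-specific analysis must. The two agree when other deaths follow the disease hazard ratio. OS looks better than the disease-only result when HRo is below 0.85, and worse when it is above. The comparison therefore carries information about other-cause deaths.

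**2. Scale.** For HRo between 0.5 and 2 the largest log shifts are ln(0.815/0.85) = -0.042 and ln(0.965/0.85) = +0.127. As a yardstick, SE(log HR) = 2/√D, which is 0.200 at D = 100 deaths and 0.141 at D = 200. Both shifts are below one standard error. At HRo = 3 the shifts are +0.119 (p = 0.05) and +0.225 (p = 0.10). The second exceeds one standard error, but an imbalance of that kind would also show in the tables of deaths by cause.

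**3. Unknown cause.** If 5% to 10% of 100 to 200 deaths lack a cause, that is 0.05 × 100 = 5 to 0.10 × 200 = 20 deaths. Suppose these are truly disease deaths and HRd = 0.85. Counting them leaves 0.85. Censoring them gives 0.85 × (1 - uA)/(1 - uB), where uA and uB are the shares of disease deaths with unknown cause in Arms A and B:

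- uA = uB = 10%: 0.85 × 0.90/0.90 = 0.85, no shift.
- uA = 15%, uB = 5%: 0.85 × 0.85/0.95 = 0.76.
- uA = 5%, uB = 15%: 0.85 × 0.95/0.85 = 0.95.

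The coding matters only if unknown causes are unbalanced between arms. All-cause OS counts each of these deaths whatever the coding.

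**4. How the SAP uses the term.** In SAP 4.3.3, SA3 makes symptomatic progression a PFS event. In SAP 4.6, the sensitivity analyses of the patient-reported endpoints add death to the event. Changing the event under this label is the SAP's own practice, so the OS analysis is not an outlier.

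**The case for a change.** The strongest case for a change is that OS is confirmatory, the SAP states in terms that only one check is planned, and that check replaces the event. Cause of death is also a judgement, whereas death is not. Protocol 6.3 allows unblinding on request after treatment is stopped, to guide later therapy, so some attributions could be made with the arm known. Relabelling the analysis, stating a rule for unknown cause, adding unstratified and eCRF-strata runs of all-cause OS and adding a cumulative-incidence table would all be cheap.

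Much of this stands as description. The analysis is a supplementary disease-specific one, it does not alone establish robustness of OS, and the rule for unknown cause is not explicit. It does not amount to a fault that needs repair:

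- A new label changes no estimate, test or conclusion.
- On a natural reading the event is defined positively, so a death not attributed to the disease is not a reported event and is censored. Censoring at death or at last known alive differs only in how long the patient stays in the risk set.
- Protocol 7.3 concerns survival status in patients lost to follow-up. It gives no ground for expecting many deaths without a cause.
- Without SAP 4.4.1.2, no visible text says whether the OS test is stratified, so it cannot be said that a stratification check is lacking or what it would vary.
- SAP 4.7.3 already provides deaths with primary cause and adverse events leading to death. An excess of toxic deaths would be seen there and would count fully in OS.

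The possibility of unblinded attribution is a reason to rest the conclusion on all-cause death, which the plan does.

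**Conclusion.** No change is called for. The description of SAP 4.4.1.3 is right, but following the plan as written leaves the OS conclusion sound: the gated test counts every death, and the disease-specific analysis carries no alpha and cannot replace it. Read beside OS, it shows whether non-disease deaths drive or dilute the result, and it should be read for that and no more.

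Under the assumed inputs (disease hazard ratio 0.85, 5% to 10% of control deaths from other causes, other-cause hazard ratio 0.5 to 2) the two analyses differ by -0.04 to +0.13 on the log scale, less than one standard error of the OS log hazard ratio at 100 to 200 deaths. Larger gaps need a threefold other-cause hazard. The unknown-cause rule is missing detail in a supportive analysis, which analysts can settle in programming. It matters only if unknown causes are unbalanced between arms. The documents give no cause-of-death rates, so these sizes are illustrative. The conclusion does not depend on them, because no choice within 4.4.1.3 touches the all-cause test.

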4.4.2. Supportive Secondary Endpoints

Objective response rate is defined as the proportion of participants who achieve a best overall response of CR or PR. Confirmation of CR and PR is not required. The ORR will be reported for both the ITT population and the subset of patients with measurable disease. The ORR with 95% CIs will be summarized for each treatment arm and compared between treatment arms using the Cochran-Mantel-Haenszel test adjusting for the randomization strata.

Clinical benefit rate is defined as the number of participants who achieve a best overall response of CR, PR, or SD \geq 6 months. Confirmation of CR and PR is not required. The CBR will be reported for both the ITT population and the subset of patients with measurable disease. The CBR with 95% CIs will be summarized for each treatment arm and compared between treatment arms using the Cochran-Mantel-Haenszel test adjusting for the randomization strata.

Disease control rate is defined as the number of participants who achieve a best overall response of CR, PR, or SD. Confirmation of CR and PR is not required. The DCR will be reported for both the ITT population and the subset of patients with measurable disease. The DCR with 95% CIs will be summarized for each treatment arm and compared between treatment arms using the Cochran-Mantel-Haenszel test adjusting for the randomization strata.

Duration of response is defined as the time from the date measurement criteria for CR or PR (whichever is first recorded) until the first date that disease is recurrent or objective progression is observed, per RECIST 1.1 criteria, or the date of death from any cause in the absence of objectively determined disease progression or recurrence. The DoR will be censored according to the same scheme as the main scheme for PFS. Median DoR with 95% CIs and curves for each treatment arm will be estimated using the Kaplan-Meier method. The analysis of DoR will be based on the participants who achieve an objective response (CR or PR) in the ITT population.

Progression-free survival by BIRC is defined the same way as the primary endpoint of PFS. For BIRC analysis, scans will be collected and reviewed for all randomized participants based on RECIST version 1.1. BIRC-assessed PFS intends to evaluate the reliability of the treatment effect based on the investigator-assessed PFS. BIRC-assessed PFS will be analyzed using the same methods as the investigator-assessed PFS. BIRC-assessed PFS is not intended to provide an alternative means of definitive analysis, but it may be useful to evaluate bias in local assessments. Discordance rates (ie, differences in assessment of progression between investigator and blinded independent central review) will be summarized for each arm (Amit et al. 2011). The agreement between BICR and investigator within a treatment arm is represented in a tabular form (Table 5). Specifically, differential discordance will be described using early discrepancy rate and late discrepancy rate differences.

| | BIRC | | |
|--------------|------------|-------|--|
| Investigator | PD | No PD | |
| PD | a=a1+a2+a3 | b | |
| No PD | С | d | |

| Table 5 BIRC-assessed Versu | s Investigator-assessed Di | sease Progression |
|-----------------------------|----------------------------|-------------------|
|-----------------------------|----------------------------|-------------------|

Abbreviations: a1 = number of agreements on timing and occurrence of PD; a2 = number of times investigators declare PD later than BIRC; a3: number of times investigators declare PD earlier than BIRC; BIRC = blinded independent review committee; PD = progressive disease.

The EDR quantifies the frequency with which the investigator assessment declares progression earlier relative to BIRC within each arm and is defined as:

$$EDR = (b+a3)/(a+b)$$

The LDR quantifies the frequency with which the investigator assessment declares progression later than BIRC within each arm and is defined as:

$$LDR = (c+a2)/(b+c+a2+a3)$$

The EDR and LDR will be summarized for each treatment arm and the differential discordance around each measure can be defined as the rate on the experimental arm minus the rate on the control arm. A negative differential discordance for the EDR and/or positive differential discordance for the LDR are suggestive of a bias in the investigator-assessed PFS favoring the experimental arm.

The ORR, CBR, DCR, and DoR by BIRC will also be summarized for each arm.

Pharmacokinetic and Exposure-Response Analyses

Pharmacokinetic analyses will be conducted on all patients who have received

- at least 1 dose of abemaciclib
- at least 1 evaluable PK sample, and
- sufficient dosing information.

Observed concentration data for each analyte will be graphically assessed and may also be summarized by time and/or dose.

Population PK modeling approaches may also be used to compute mean PK parameters (for example, clearance, exposure, volume of distribution) and interindividual PK variability.

A separate Population PK and Exposure-Response Analysis Plan will describe the planned PK and exposure-response analyses.

4.5. Exploratory Endpoints Analysis

4.6. Patient-Reported Outcomes Analyses

The PROs will be used to compare changes in cancer-related symptoms, physical function, **CCI** outcomes between treatment arms and **CCI**

CC The analyses for PROs will be conducted in the ITT population. The following PRO instruments are utilized:

- "Worst pain single item" NRS
- CCI
- EORTC IL-19: Physical Function
- CCI
- mBPI-SF
- CCI

Time to sustained worsening of worst pain (based on the Worst Pain NRS) is defined as the time from randomization to the first increase (≥ 2 points) in the weekly average of the worst pain score with confirmation in the next consecutive week. Participants not known to have sustained worsening will be censored at the last documented assessment. Time to sustained worsening of worst pain will be summarized for each arm by the Kaplan-Meier method and will be compared between the arms using the stratified log-rank test. Additional cutoff values of increase (eg, ≥ 3 points, ≥ 4 points) may be explored as sensitivity analyses if deemed appropriate. Sensitivity analysis will be done by including death as part of the event definition. Additional sensitivity analyses for time to worsening without confirmation in the next consecutive week may be performed if deemed appropriate. Analgesic use will be summarized descriptively by cycle. The WHO-Analgesic Ladder (Jadad and Brownman 1995) may be used to provide supportive interpretation of the pain endpoint in a sensitivity analysis.

Time to worsening of physical function (based on either CCI

or EORTC IL-19) is defined as the time from randomization to the first \geq 10-point decrease from baseline with confirmation at the next cycle. Participants not known to have worsening will be censored at the last documented assessment. Sensitivity analysis will be done by including death as part of the event definition. Time to worsening of physical function will be summarized for each arm by the Kaplan-Meier method, and the stratified log-rank test will be used to compare between the 2 arms.

Compliance will be assessed for each instrument. The compliance rate by instrument will be calculated at baseline, per week (if appropriate) and per cycle and overall, with reasons for noncompliance to be reported. The number of participants with expected assessments at each post-baseline visit is the number of participants who have received the study drugs in a previous visit and will be used as a denominator, the number of participants who completed assessments will be used as a numerator for calculating a compliance rate. For the Worst Pain NRS, participants will be considered compliant if they have completed \geq 50% of the daily assessments during each period (ie, week) and will be reported for each cycle. A 7-day average score regardless of dosing will be calculated for each consecutive week starting from Cycle 1 Day 2, if

the participant is compliant for the period (completed 4 days out of the 7-day period). For other instruments, the reason and number of missing and incomplete questionnaires and/or assessments by visit will be summarized for each instrument and treatment arm.

The Cycle 1 Day 1 (pre-dose) visit will be considered as baseline for all PRO analyses. The analysis for change from baseline will be based on the participants who have baseline and at least 1 post-baseline data. Other PRO analyses will be described in a separate PRO SAP.

4.7. Safety Analyses

The safety analyses will be conducted in the safety population.

4.7.1. Extent of Exposure

Drug exposure, dose intensity, and drug adjustment (dose omissions, increases, reductions, interruptions, and delays) for abemaciclib/placebo and fulvestrant will be summarized for all treated patients per treatment arm. Drug exposure will include summaries of cycles received per patient, duration on therapy, and cumulative dose. Dose intensity will be calculated as the actual cumulative amount of drug taken divided by the duration of treatment. Relative dose intensity will be calculated as the actual amount of drug taken divided by the amount of drug prescribed times 100% (expressed as a percentage).

For abemaciclib/placebo, extent of exposure will be measured by pill counts and summarized cumulatively. The summary will include total dosage taken, dose intensity, and relative dose intensity. The assigned cumulative dose for each patient during each cycle is 150 mg per dose \times 2 doses per day \times 28 days = 8400 mg. The assigned cumulative dose while on study is 150 mg per dose \times 2 doses per day \times number of days on treatment.

For fulvestrant, extent of exposure will be measured using the fulvestrant administration eCRF and summarized by cycle and cumulatively. The summary will include total dosage administered, dose intensity, and relative dose intensity. The assigned cumulative dose for each patient during each cycle is 1000 mg for Cycle 1 and 500 mg for Cycle 2 and beyond. The assigned cumulative dose while on study is 500 mg + 500 mg × number of cycles started.

Dose adjustments and omissions, along with the reason for adjustment or omission, will be summarized for abemaciclib/placebo and fulvestrant.

